- i A COVID-19 PCR test will be performed at Screening and on Day -1 prior to dosing. If test results are positive for the virus the participant will be excluded from the study.
- j A serum pregnancy will be performed at screening. Urine pregnancy tests may be performed at all other visits. If a urine test result is positive, the result will be confirmed with a serum test.
- k A serum FSH test will be performed in women at screening to confirm postmenopausal status.
- l If the HCV antibody test is positive, it must be followed by an HCV RNA test. Participants who are positive for HCV antibody and negative for HCV RNA may be enrolled. See Exclusion Criterion #8, Section 5.2.
- m Single 12-lead ECG at screening, safety follow-up and ET visit. Three triplicate 12-lead ECGs at pre-dose 2 minutes apart to establish baseline. Triplicate 12-lead ECGs at all other scheduled times. The actual day and time must be documented in the CRF.
- n PK samples identified with an X may be obtained at any time within the scheduled days; the exact date and time of blood sample collection must be recorded in the CRF.
- o Lipid panel: TG, total cholesterol, LDL-C (PUC), VLDL-C (calculated), HDL-C, non-HDL-C (calculated).

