### **7.1.2. QTcF Stopping Criteria**

If a clinically significant finding is identified on ECG, including, but not limited to changes from Day 1 predose baseline in QT interval corrected using Fridericia's formula [QTcF] after enrollment, the Investigator or qualified designee will determine if the participant can continue in the study and if any change in participant management is needed. QTcF > 500 confirmed from the average of triplicate ECGs is a criterion to stop dosing in a participant. This review of the ECG printed at the time of collection must be documented. Any new clinically relevant finding should be reported as an AE. The predose baseline used for the calculation of the change in QTc value is the average of the triplicate ECG taken closest to the time point of dosing on Day 1.

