### 8.2.3. Electrocardiograms

Triplicate 12-lead ECGs will be obtained on the days and times specified in the SoA (Section 1.3). ECGs will be recorded using an ECG machine that automatically calculates the heart rate and measures PR, QRS, QT, and QTc intervals. Refer to Section 7.1.2 for QTc withdrawal criteria and any additional QTc readings that may be necessary:

- At each time point at which triplicate ECG are required, 3 individual ECG tracings should be obtained as closely as possible in succession, but at least 1 minute apart.
- The ECGs must be recorded before collecting any blood samples. Participants must be supine for at least 5 minutes before ECG collection and remain supine but awake during ECG collection. ECGs may be obtained at additional times, when deemed clinically necessary. Collection of additional ECGs at a particular time point is allowed to ensure high-quality records.

ECGs will be interpreted by a qualified physician, the Investigator, or qualified designee at the site as soon after the time of ECG collection as possible. Ideally, the Investigator should be present:

- To determine whether the participant meets entry criteria at screening; and
- For immediate participant management, should any clinically relevant findings be identified.

If a clinically significant finding is identified (including, but not limited to, changes in QT/QTc interval from baseline) after enrollment, the Investigator will determine if the participant can continue in the study (Section 7.1.2). The Investigator, or qualified designee, is responsible for determining if any change in participant management is needed and must document his/her review of the ECG printed at the time of evaluation. Any new clinically relevant finding should be reported as an AE.

The machine-read ECG intervals and heart rate may be used for data analysis and report writing purposes unless the Investigator considers there is a need for over-read of the ECGs prior to completion of the final study report (in which case the overread data would be used).

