### 5.2.2 Baseline

In Part A, baseline is defined as the last non-missing value (either scheduled, unscheduled or repeat) before the participant receives the first dose of study drug.

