## 5.2.7 Electrocardiogram (ECG) Data

For ECG data recorded on continuous scales, if replicate (i.e., triplicate) values are recorded at a time point, the mean or the replicates rounded to the integer will be used for summarization. For overall interpretation if more than one value is recorded, the most severe (worst case) of the respective readings will be taken.

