### 5.11.6 Electrocardiogram Data

Descriptive statistics for observed values and changes from baseline in the following ECG variables will be tabulated at each follow-up:

- Heart rate (bpm)
- PR interval (ms)
- QRS complex (ms)
- QT interval (ms)
- QTc interval (ms)
- QTcF interval (ms) [Fridericia's formula]
- QTcB interval (ms) [Bazett's formula]
- RR interval (ms)

QMD Ref: Worldwide-TMP-ST-054-1.0_Effective: 12Aug2022	Governing QMD: Worldwide-SOP-ST-026
Confidentiality Statement This document is the property of Worldwide Clinical Trials Inc. and may not be duplicated, copied, altered or removed from company without prior approval from Worldwide Quality Assurance or in compliance with Worldwide Standard Operating Procedures.	

Worldwide Clinical Trials Controlled Quality Management Document		
 WORLDWIDE CLINICAL TRIALS	Sponsor:	Eli Lilly and Company
	Protocol Number:	J4N-MC-YFAA
STATISTICAL ANALYSIS PLAN		

Number and percentage of subjects that meet each of the following categories will be presented:

- Largest postdose assessment of QTcF > 450
- Largest postdose assessment of QTcF > 480
- Largest postdose assessment of QTcF > 500
- Largest QTcF change from baseline > 30
- Largest QTcF change from baseline >60

Shift tables in relation to the overall interpretation (Normal; Abnormal Not Clinically Significant [NCS], and Abnormal Clinically Significant [CS]) from baseline to each follow-up visit will be presented.

The relationship between plasma PK concentrations of LY3885125 and  $\Delta$ QTcF will be quantified using a linear mixed-effects modelling approach. The model will have  $\Delta$ QTcF as the dependent variable, plasma PK concentrations of LY3885125 as the explanatory variate (0 for placebo), baseline QTcF as an additional covariate, study treatment (active = 1 or placebo = 0) and time (i.e., post-dose time point: categorical) as fixed effects, and random effects on intercept and slope per participant. In all calculations, concentrations in participants who received placebo will be set to zero. LY3885125 plasma PK concentrations below the quantifiable limit at pre-dose will be set to zero and after dosing will be set to 1/2 the lower limit of quantitation in the concentration-QTc analysis.

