An unstructured covariance matrix will be specified for the random effects. If convergence cannot be achieved even after appropriate rescaling of the concentrations, the random effect on the slope and intercept will be dropped, in this order, until convergence is achieved. The degrees of freedom (df) estimates will be determined by the Kenward-Roger method. From the model, the slope (i.e., the regression parameter for the concentration) and the treatment effect-specific intercept (defined as the difference between active and placebo) will be estimated together with the 2-sided 90% CI. The estimates for the time effects will be reported with standard error (SE).

The following SAS codes can be used to conduct the LME model in the example:

```
proc mixed data=PKQTc method=reml;
  class USUBJID AVISTPT;
  model  $\Delta$ QTcF=PRTAN CONC1 AVISTPT CBASE / solution cl noint alpha=0.1
    alphap=0.1 covb ddfm=kr;
  random int CONC1 / type=un subject=USUBJID s;
run;
```

Throughout the LME modelling, for any timepoints where triplicate values are collected for QTcF, then the arithmetic average of the triplicates should be analysed.

QMD Ref: Worldwide-TMP-ST-054-1.0_Effective: 12Aug2022	Governing QMD: Worldwide-SOP-ST-026
Confidentiality Statement	
This document is the property of Worldwide Clinical Trials Inc. and may not be duplicated, copied, altered or removed from company without prior approval from Worldwide Quality Assurance or in compliance with Worldwide Standard Operating Procedures.	

Worldwide Clinical Trials Controlled Quality Management Document		
 WORLDWIDE CLINICAL TRIALS	Sponsor:	Eli Lilly and Company
	Protocol Number:	J4N-MC-YFAA
STATISTICAL ANALYSIS PLAN		

A scatter plot of QTcF data vs LY3885125 plasma PK concentration will also be presented for all timepoints where an ECG and PK sample were drawn within the same 10 minute window, with unique formatting for each treatment group.

All ECG data, including details of any abnormalities, will be listed.

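### The SAP has no ECG-specific baseline: QTcF change is normally measured from the last pre-dose triplicate rather than from all pre-dose tracings, and rounding before strict cut-offs can only undercount

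*SAP*

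**What the plan says.** Three places bear on the QTcF baseline.

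- SAP 5.2.2, for all Part A variables: "baseline is defined as the last non-missing value (either scheduled, unscheduled or repeat) before the participant receives the first dose of study drug". There is no exception for ECGs.
- Protocol 1.3.1, footnote m: "Three triplicate 12-lead ECGs at pre-dose 2 minutes apart to establish baseline". Read literally, this is nine tracings.
- Protocol 7.1.2: the baseline for change in QTc "is the average of the triplicate ECG taken closest to the time point of dosing on Day 1". That is three tracings.

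On replicates, SAP 5.2.7 says that "the mean or the replicates rounded to the integer will be used for summarization". For the concentration-QTc model, SAP 5.11.6 says that where triplicates exist "then the arithmetic average of the triplicates should be analysed", and it mentions no rounding. The QTcF category table in 5.11.6 has three absolute rows, starting with "Largest postdose assessment of QTcF > 450", and two change rows, starting with "Largest QTcF change from baseline > 30". SAP Section 8 declares no changes from the protocol analysis.

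**The concern.** Averaging reduces noise, and baseline noise is carried into all of a participant's changes. If the last triplicate happens to be low, every post-dose change is too high by the same amount, and one participant can cross 30 ms without any drug effect. In dose groups of 6 or 9 active participants, one spurious case is 17% or 11% of the group. The protocol schedules further pre-dose triplicates for this purpose, yet the SAP does not say how they are combined. The last-value rule also admits unscheduled and repeat records, so one stray tracing just before dosing would become the baseline.

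Rounding is a separate matter. If triplicate means are made whole numbers before a strict greater-than test, the safety table can disagree with Protocol 7.1.2, which refers to a triplicate average above 500.

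**Working it through.** **Inputs from the documents.** Pre-dose tracings: 3 × 3 = 9 under footnote m, against 3 under Protocol 7.1.2. Part A size: Protocol 9.5 gives approximately 68. The allocation ratios reproduce this: 2 × (6 + 2) + 3 × (9 + 2) + (10 + 9) = 16 + 33 + 19 = 68. Cohort 6 was not enrolled (SAP Section 3), which leaves 49. The 49 is inferred, because cohort sizes are redacted in the design tables. No QTcF SD or ECG precision target is stated.

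**Assumptions.** No drug effect. Within-participant SDs in ms: slow drift s, triplicate-level t, tracing-level r, set to (5, 3, 5), (6, 3, 6) and (7, 4, 7).

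**Formula.** Variance of change = 2s² + t² + r²/3 + B, where B is the baseline error:
- last triplicate: B = t² + r²/3
- nine tracings, triplicate-level error independent: B = t²/3 + r²/9
- nine tracings, triplicate-level error shared: B = t² + r²/9
- one stray tracing: B = t² + r²

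For (5, 3, 5) the common part is 50 + 9 + 8.33 = 67.33. Adding B gives 67.33 + 17.33 = 84.67 for the last triplicate, 67.33 + 5.78 = 73.11 for nine independent, 67.33 + 11.78 = 79.11 for nine shared, and 67.33 + 34 = 101.33 for one tracing.

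| (s, t, r) | Last triplicate | Nine, shared | Nine, independent | One tracing |
|---|---|---|---|---|
| (5, 3, 5) | 84.67 | 79.11 (−6.6%) | 73.11 (−13.7%) | 101.33 (+19.7%) |
| (6, 3, 6) | 114.00 | 106.00 (−7.0%) | 100.00 (−12.3%) | 138.00 (+21.1%) |
| (7, 4, 7) | 162.67 | 151.78 (−6.7%) | 141.11 (−13.3%) | 195.33 (+20.1%) |

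On the SD scale the gain over the last triplicate is 3.3–3.6% (shared) or 6.3–7.1% (independent). Some sharing is likely. Protocol 8.2.3 says that "3 individual ECG tracings should be obtained as closely as possible in succession, but at least 1 minute apart", so a set spans at least 2 minutes. If the 2 minutes in footnote m separates sets, three sets fit in about 3 × 2 + 2 × 2 = 10 minutes at minimum spacing.

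**Wider grid** (r 4–10, t 0–6, correlation between sets 0–1, extra within-participant SD 0 or 8 ms): the SD of change falls by 1.2% to 18.4%. The upper end is 1 − √((1 + 1/3)/2), with every error independent and no extra variation. The lower end is 12.11 to 11.96 ms.

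**False >30 ms cases.** Simulating 100,000 participants with 10 post-dose triplicates (assumed) and independent triplicate-level error, the chance of any change above 30 ms is 0.5%, 1.9% and 6.3% with the last triplicate and 0.2%, 1.2% and 4.4% with nine tracings. The drop is 0.3 to 1.9 percentage points, or 49 × 0.003 = 0.15 to 49 × 0.019 = 0.93 participants. It is smaller if the error is shared.

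**Rounding.** With whole-millisecond tracings, rounding moves a triplicate mean by −1/3, 0 or +1/3. The error variance is 2/27, so the SD is 0.27 ms per value and √(4/27) = 0.38 ms per change. On the wider grid this adds at most 0.7% to the SD of change. At the cut-offs, 450.33, 480.33 and 500.33 become 450, 480 and 500 and are not counted. A true change of 431.33 − 400.67 = 30.67 becomes 431 − 401 = 30. The reverse cannot happen: no value at or below a whole-number cut-off rounds above it. If the largest QTcF has mean 415–435 and SD 20 (assumed), the chance of falling between 450 and 450.5 is 0.0021–0.0075, or 0.1–0.4 of 49 participants.

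**The case against.** The strongest reply is that the SAP already follows the protocol. Protocol 7.1.2 states a baseline for QTc change, and SAP 5.2.2 with 5.2.7 reproduces it whenever the last pre-dose record is a triplicate. That stands. The unresolved conflict is between footnote m and 7.1.2, and a reader who infers that the SAP departs from the protocol goes too far.

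A reader might also infer that two thirds of the baseline data are thrown away. The documents do not establish this. The pre-dose timing cells are redacted, and if all sets share one nominal time point, 5.2.7 can be read as averaging them. Nine is itself a reading of footnote m. The contrast with plain triplicates at other times, and the reference in 7.1.2 to the closest triplicate, both favour it. If only one triplicate were taken, the precision gain would disappear, and the stray-tracing and rounding points would remain.

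It is also fair that the affected outputs are secondary. The primary endpoints are adverse events, and Protocol 9.3.5 plans no statistical comparison of safety endpoints. In the concentration-QTc model, the baseline covariate and the random intercept absorb part of a baseline error common to all of a participant's changes, so the 7–14% does not carry over in full. On rounding, 5.2.7 speaks of summarization and does not name the cut-off tests. However, SAP Section 10 titles the threshold table as descriptive statistics, so the rounding rule plausibly reaches it.

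**Conclusion.** The point holds as a modest, inexpensive improvement and a clarification. Averaging all scheduled pre-dose tracings is never noisier than the last triplicate under the models examined. The gain in the variance of QTcF change is about 7% to 14% on the main assumptions. Every variance component is assumed, and the wider grid shows how far the figure can move. The direction does not depend on those values.

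Three stronger readings should be set aside. Not every outlier count is affected, because the >450, >480 and >500 rows do not use baseline. The roughly 20% variance penalty of a single-tracing baseline is not the planned rule; it arises only when an unscheduled or repeat single ECG is the last record before dosing. Rounding is not a meaningful source of noise; its harm is a rare undercount at strict cut-offs. It also does not alter the participant-level criterion in Protocol 7.1.2, which the investigator applies outside the SAP.

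**What to change.** 1. In SAP 5.2.2, define the ECG analysis baseline as the unrounded arithmetic mean of all scheduled Day 1 pre-dose tracings. Allow an unscheduled or repeat single tracing only when no scheduled triplicate is available.
2. Use that baseline throughout SAP 5.11.6: change summaries, the >30 and >60 ms rows, and both the change and the baseline covariate in the concentration-QTc model.
3. In SAP 5.2.7, apply all cut-offs to unrounded means and round for display only.
4. Reconcile footnote m with Protocol 7.1.2, and record in SAP Section 8 that the analysis baseline differs from the one in 7.1.2 and why. The participant-level stopping rule is left as it stands.

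The cost is SAP wording, a short reconciliation note and minor programming. No new measurements are needed if the scheduled tracings were taken. If the Part A database is already locked, SAP Section 5 provides for an addendum.

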### 5.2.3 Early Terminations Assessments

Early termination assessments will be excluded from tabulations and will be listed only.

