Abbreviations: AE = adverse event; ApoB = apolipoprotein B; BP = blood pressure; COVID-19 = Coronavirus disease 2019; CRF = case report form; CRU = clinical research unit; D = day; ECG = electrocardiogram; ET = early termination; h = hour(s); FSH = follicle-stimulating hormone; HCV = hepatitis C virus; HDL-C = high-density lipoprotein cholesterol; I/E = inclusion/exclusion; ISR = injection-site reaction; LDL-C = low-density lipoprotein cholesterol; CCI min = minutes; P = predose; PCSK9 = proprotein convertase subtilisin/kexin type 9; PCR = polymerase chain reaction; PD = pharmacodynamics; PE = physical examination; PK = pharmacokinetics; PR = pulse rate; Q2W = once every 2 weeks; PUC = preparative ultracentrifugation; Q4W = once every 4 weeks; RR = respiration rate; SC = subcutaneous; TEAE = treatment-emergent AE; TG = triglyceride; VAS = visual analog score; VLDL-C = very low-density lipoprotein cholesterol.

- a All follow-up visits should take place in the morning after an overnight fast of at a minimum **CCI** hours. Water is permitted *ad libitum* during the fasting period.
- b After Day **CCI**, once any treatment related AEs are resolved and PCSK9 levels return to at least **CCI**% of baseline, the Monitoring Extension visits may be discontinued. The final visit of a participant who completes the study will be the first scheduled Monitoring Extension visit after they report no ongoing AEs, and after PCSK9 levels have returned to at least 80% of baseline in a blood sample collected at one of the preceding visits. At the participant's final visit, they will receive the assessments performed at ET, except for the collection of a blood sample for PCSK9 assessment.
- c Outpatient follow-up visits on Days **CCI** will be conducted through a remote telehealth visit assessing AE/concomitant medications.
- d On Day -1 prior to randomization review AEs, concomitant medications, and compliance to Inclusion/Exclusion criteria.
- e Discharge from CRU after all assessments have been completed.
- f All doses of study intervention will be administered SC in the morning after an overnight fast of approximately 8 hours duration.
- g Complete physical examination performed at Screening, ET and last visit., and symptom-directed examinations at all other visits.
- h Body weight is measured at any time before breakfast.

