## 5.2.8 Unscheduled Visits

Only scheduled post-baseline laboratory and vital signs values will be tabulated unless otherwise stated. Post-baseline repeat / unscheduled assessments will be included in all listings in the relevant appendices to the CSR.

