### 5.2.10 Classification of ADA

Subjects are classified according to the following table for ADA.

ADA category	Criteria
Subjects with baseline immunogenicity data	Subjects with a valid ADA assessment at baseline
Subjects with post-baseline immunogenicity data	Subjects with any valid ADA assessment post-baseline

QMD Ref: Worldwide-TMP-ST-054-1.0_Effective: 12Aug2022	Governing QMD: Worldwide-SOP-ST-026
Confidentiality Statement This document is the property of Worldwide Clinical Trials Inc. and may not be duplicated, copied, altered or removed from company without prior approval from Worldwide Quality Assurance or in compliance with Worldwide Standard Operating Procedures.	

Worldwide Clinical Trials Controlled Quality Management Document		
 WORLDWIDE CLINICAL TRIALS	Sponsor:	Eli Lilly and Company
	Protocol Number:	J4N-MC-YFAA
STATISTICAL ANALYSIS PLAN		

ADA category	Criteria
Subjects with baseline and post-baseline immunogenicity data	Subjects with both a valid ADA assessment at baseline and any valid ADA assessment post-baseline
Subjects with baseline or post-baseline immunogenicity data	Subjects with any valid ADA assessment at baseline or post-baseline
ADA+ prevalence at baseline	Subjects with a positive ADA assessment at baseline
ADA+ prevalence at post-baseline	Subjects with any positive ADA assessment post-baseline
ADA+ prevalence at both baseline and post-baseline	Subjects with both a positive ADA assessment at baseline and any positive ADA assessment post-baseline
ADA Positive at baseline or post-baseline	Subjects with any positive ADA assessment at baseline or post-baseline
Treatment-Emergent ADA+	Treatment-boosted ADA+; or treatment-induced ADA+
Treatment-boosted ADA+	Subjects who were ADA positive at both baseline and post-baseline, but had an increase in ADA titer from baseline to post-baseline
Treatment-induced ADA+	Subjects who were ADA negative or missing at baseline and became ADA positive post-baseline

ADA prevalence is defined as the proportion of subjects in category “ADA Positive”.

ADA incidence is defined as the proportion of subjects in category “Treatment-Emergent ADA+”.

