	14.3.4.6.3	Safety ECG Data, Overall Interpretation Shift from Baseline to Worst Post Baseline, Part A – Safety Analysis Set	IP	-
	14.3.4.7.1	Prior Medications by ATC Level 3 and Preferred Name, Part A – Full Analysis Set	IP	-
	14.3.4.7.2	Concomitant Medications by ATC Level 3 and Preferred Name, Part A – Full Analysis Set	IP	14.3.4.7.1
	14.3.4.8.1	PCSK9 Data, Descriptive Statistics for Observed Values and Change from Baseline, Part A – PD Analysis Set	IP	-
	14.3.4.8.2	Apo Panel Data, Descriptive Statistics for Observed Values and Change from Baseline, Part A – PD Analysis Set	IP	14.3.4.8.1
	14.3.4.8.3	CCI [REDACTED] [REDACTED] [REDACTED] – [REDACTED]	IP	14.3.4.8.1
	14.3.4.9	Linear Mixed-Effects Model for Plasma PK Concentrations of LY3885125 and ΔQTcF, Part A – PK Analysis Set	Stat IP	-
	14.3.4.10	Summary of Immunogenicity Parameters by Treatment Group – Immunogenicity Analysis Set	IP	-
14.4.1	PK Analysis			
	14.4.1	Descriptive Statistics for Concentration-Time Data of LY3885125 in Plasma after Single Ascending Subcutaneous Doses of LY3885125 – PK Analysis Set	IP	-

QMD Ref: Worldwide-TMP-ST-054-1.0_Effective: 12Aug2022	Governing QMD: Worldwide-SOP-ST-026
Confidentiality Statement This document is the property of Worldwide Clinical Trials Inc. and may not be duplicated, copied, altered or removed from company without prior approval from Worldwide Quality Assurance or in compliance with Worldwide Standard Operating Procedures.	

Worldwide Clinical Trials Controlled Quality Management Document		
 WORLDWIDE CLINICAL TRIALS	Sponsor:	Eli Lilly and Company
	Protocol Number:	J4N-MC-YFAA
STATISTICAL ANALYSIS PLAN		

Section Number	Table Number	Table Title	Validation Method	Shell Number (if repeat)
	14.4.2	LY3885125 Plasma Pharmacokinetic Parameters after Single Ascending Subcutaneous Doses of LY3885125 – PK Analysis Set	IP	-
	14.4.3	Amount of LY3885125 Excreted in Urine per Collection Interval – PK Analysis Set	IP	-
	14.4.4	Percentage of LY3885125 Dose Excreted in Urine per Collection Interval – PK Analysis Set	IP	-
	14.4.5	LY3885125 Urine Pharmacokinetic Parameters after Single Ascending Subcutaneous Doses of LY3885125 – PK Analysis Set	IP	-
	14.4.6	Dose-Proportionality Assessment of LY3885125 in Plasma after Single Ascending Subcutaneous Doses of LY3885125 – PK Analysis Set	MR	-

QMD Ref: Worldwide-TMP-ST-054-1.0_Effective: 12Aug2022	Governing QMD: Worldwide-SOP-ST-026

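### SAP 5.2.3 keeps early-termination results out of all tables, in conflict with outputs defined on the largest QTcF, the worst ECG and any positive ADA result

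*SAP*

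**What the plan says.** SAP 5.2.3 is a single sentence: "Early termination assessments will be excluded from tabulations and will be listed only". It carries no exception and no cross-reference.

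Three planned outputs are defined per participant across the whole post-dose period:

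- **QTcF categories** (SAP 5.11.6, Table 14.3.4.6.2). These are counts and percentages for items such as "Largest postdose assessment of QTcF > 500" and "Largest QTcF change from baseline >60".
- **ECG interpretation shift** (Table 14.3.4.6.3). The title in SAP section 10 reads "Overall Interpretation Shift from Baseline to Worst Post Baseline". The text of 5.11.6 instead describes shifts to each follow-up visit separately.
- **ADA status** (SAP 5.2.10, Table 14.3.4.10). Post-baseline prevalence is "Subjects with any positive ADA assessment post-baseline". The treatment-induced and treatment-boosted categories build on post-baseline positivity.

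The Part A schedule (Protocol 1.3.1) marks a 12-lead ECG in the ET column, and footnote m says it is a single tracing. The immunogenicity row has an entry in the ET column, but it is redacted.

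SAP 5.3 bases percentages on the column-header N unless a footnote says otherwise. SAP 5.1.6 admits a participant to the Immunogenicity Analysis Set on a baseline sample alone.

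**The concern.** Leaving ET values out of by-visit rows is ordinary practice, because an ET visit belongs to no nominal time point. That reason does not carry over to a maximum, a worst value or an any-occurrence rule, which are meant to use everything observed after dosing. The SAP gives no order of precedence. A programmer who follows 5.2.3 drops ET values from these outputs, and one who follows the output definitions keeps them. The same data could then yield two different safety tables.

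Under the literal reading the participant is not treated as missing. The denominator is unchanged, so an ET-only exceedance or conversion is tabulated as a non-event. This sits oddly with the SAP's other conventions, which resolve doubt conservatively: AEs of unclear timing count as treatment-emergent (5.2.5.1), missing severity becomes severe and missing causality becomes related (5.11.1), and the worst of replicate ECG interpretations is used (5.2.7).

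Late observations also matter for this product. Protocol 4.3.4 expects the maximum effect weeks after dosing and a return to baseline that may take months. For someone who leaves follow-up early, the ET visit may be the last or only late observation.

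**Working it through.** **1. Group sizes.** Cohort sizes are masked or garbled in the public tables, so they are read from the allocation ratios in Protocol 4.1.1 and checked against the total in Protocol 9.5.

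- All six cohorts: 2 × (6 + 2) + 3 × (9 + 2) + (10 + 9) = 16 + 33 + 19 = 68. This matches the protocol's approximate 68.
- SAP section 4 says only Cohorts 1 to 5 were run: 68 − 19 = 49.
- Active: 2 × 6 + 3 × 9 = 39. Pooled placebo: 5 × 2 = 10.

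**2. Direction.** Removing observations from a maximum, a worst value or an any-rule can only lower the count or leave it unchanged. Within a group, the literal rule therefore cannot overstate these incidences.

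**3. Effect of one ET-only event.** The tabulated percentage falls by 1/n. Exact 95% upper limits are added to show what it does to the inference. For 0/n the limit is 1 − 0.025^(1/n). For 1/n it is the 0.975 quantile of Beta(2, n − 1). The SAP does not plan these intervals.

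| Group | n | ET left out | ET counted | Upper limit, 0/n | Upper limit, 1/n |
|---|---|---|---|---|---|
| Dose level, Cohorts 1–2 | 6 | 0% | 16.7% | 45.9% | 64.1% |
| Dose level, Cohorts 3–5 | 9 | 0% | 11.1% | 33.6% | 48.2% |
| Pooled active | 39 | 0% | 2.6% | 9.0% | 13.5% |
| Pooled placebo | 10 | 0% | 10.0% | 30.8% | 44.5% |

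**4. How often ET might occur.** The documents give no rate, so 5%, 10% and 20% are assumed. The expected number of ET participants among 39 active is 39 × r, or 2.0, 3.9 and 7.8. The chance of at least one is 1 − (1 − r)^39, or 87%, 98% and over 99%. This is the chance that someone terminates early. It is not the chance of an ET-only event, for which the documents offer no basis.

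**5. Is there an escape clause?** The only qualifier of that kind is in SAP 5.2.8: "Only scheduled post-baseline laboratory and vital signs values will be tabulated unless otherwise stated". It concerns unscheduled laboratory and vital-sign values, names neither ECG nor ADA, and does not modify 5.2.3. SAP section 8 declares no changes to the protocol's analysis.

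**The case against.** The best counter-argument is that a specific definition overrides a general convention. On that view the largest post-dose value and any positive sample already include ET, and only a clarification is missing. This is a possible reading, but the SAP states it nowhere, and 5.2.3 is worded absolutely. It makes exclusion uncertain without removing the conflict.

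Other points stand in part:

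- **Results are not lost.** ECG and immunogenicity data are listed (16.2.8.7 and 16.2.8.11). AE tables keep events up to the ET visit (SAP 5.11.1), and new clinically relevant ECG findings are to be reported as AEs (Protocol 7.1.2 and 8.2.3). The concern therefore does not reach every table. QTcF threshold counts and ADA conversions have no guaranteed route of that kind.
- **The ECG shift is disputed.** If 5.11.6 governs over the table title, that output is by visit and leaving ET out is unremarkable.
- **Precision differs.** The ET ECG is a single tracing, whereas the baseline uses triplicates, and the over-500 criterion in Protocol 7.1.2 requires an averaged triplicate. Footnote m also specifies single tracings at safety follow-up, so this calls for a footnote, not exclusion.

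Three stronger inferences are tempting but unsupported:

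- **Completers lose their closing assessments.** The schedule does say "At the participant's final visit, they will receive the assessments performed at ET", but the same footnote defines that visit as a scheduled one in the Monitoring Extension. It borrows the ET procedures, and nothing suggests it takes the ET label.
- **Section 5.2.8 creates the same problem for laboratory and vital-sign values**, since unscheduled values may set the baseline. The SAP plans no worst-value laboratory or vital-sign table, so no planned output of that kind is affected.
- **Early leavers are those most likely to have had a safety problem.** Part A is a single dose, so early termination means leaving follow-up, which may happen for any reason (Protocol 7.2). The rule also applies equally to placebo, so no between-group bias is shown.

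**Conclusion.** The conflict is real and limited. SAP 5.2.3, taken as written, cannot be squared with the QTcF-category and ADA definitions, nor with the title of Table 14.3.4.6.3. If it is followed, an exceedance or conversion seen only at ET is tabulated as a non-event, at a cost of 16.7 percentage points per event in a group of 6 and 11.1 in a group of 9.

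This rests on four conditions: cohort sizes equal to the allocation ratios, column-header denominators with no overriding footnote in the table shells, at least one ET-only event, and, for ADA, a redacted ET cell that stands for a sample. The documents give neither the number of early terminations nor any sign that such an event occurred. The finding is therefore about an unresolved rule and does not show that any reported result is wrong. With so few participants per dose it is worth settling.

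**What to change.** - Limit SAP 5.2.3 to by-visit summaries. State that ET assessments are included in the largest-value, worst-post-baseline and any-post-baseline derivations, namely the QTcF categories, the ECG worst shift and the ADA categories.
- Add a footnote to the ECG tables that the ET ECG is a single tracing.
- Reconcile the shift described in SAP 5.11.6 with the title of Table 14.3.4.6.3, so that text and shell name the same output.

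The cost is a few sentences and minor reprogramming, with no new data. SAP section 5 requires approval of the SAP and shells before Part A database lock. If lock has passed, the same section routes the change to a post-lock addendum.
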